ID: 2019ZY004-MERIDIAN

Research title:

A study on the microcirculatory characteristics of meridian phenomenon for the heart and lung meridians based on patients with chronic obstructive pulmonary disease

Date: March 25, 2019

Study Protocol

Part1. Study introduction and objectives

(1) Brief introduction

This study will include 40 patients with chronic obstructive pulmonary disease (COPD), and 80 healthy volunteers. Laser doppler examination will be adopted to assess the microcirculatory characteristics of meridian phenomena and investigate the site specificity for the meridian-visceral association and surface-surface association between two specific meridians.

(2) Study objects

1) This study aims to detect the microcirculatory characteristics of meridian phenomena using laser doppler flowmetry(LDF). Thus, the biological characteristics of meridian phenomenon could be presented objectively in a scientific methodology.

2) This study aims to investigate the site specificity for the meridian-visceral association and surface-surface association between two specific meridians.

Part2. Study program

1.Study subjects

The subjects of this study include two kinds of participants, which includes healthy volunteers and patients with COPD.

1.1 Diagnostic criteria

1.1.1 Diagnostic criteria for COPD

The diagnostic criteria of COPD is based on “The diagnosis and treatment guidelines of chronic obstructive pulmonary disease” by the Thoracic Society of Chinese Medical Association in 2013 and “the Global Initiative for Chronic Obstructive Lung Disease (GOLD)” in 2017. The clinical symptoms include dyspnea, chronic cough and expectoration. Patients often have a history of exposure to various risk factors. And persistent airflow obstruction is indicated by the pulmonary function test (post-bronchodilator $FEV_1 / FVC < 0.70$). In addition, other possible diseases are excluded.

1.2 Inclusion criteria

1.2.1 Inclusion criteria for COPD

(1) Patients should meet the above diagnostic criteria, and the severity of COPD is in the stage of GOLD 2 or 3 based on pulmonary function testing;

(2) COPD patients in the stable phase, who present with mild symptoms of cough, expectoration and short breath;

(3) $35 \leq \text{age} \leq 75$ years, male or female;

(4) Patients have clear consciousness and could communicate with others normally;

(5) Patients could understand the full study protocol and have high adherence. Written informed consent is signed by themselves or their lineal kin.

1.2.2 Inclusion criteria for health volunteers

(1) Healthy volunteers who could provide a recent medical examination report to confirm they have not any cardiovascular, respiratory, digestive, urinary, hematological, endocrine and neurological disease;

(2) $\text{age} \geq 20$ years, male or female;

(3) Participants have clear consciousness and could communicate with others normally;

(4) Participants could understand the full study protocol and have high adherence. Written informed consent is signed by themselves or their lineal kin.

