1.3.2 Exclusion criteria of health volunteers

(1) Participants have mental illness, severe depression, alcohol dependence or history of drug abuse;

(2) Pregnant or lactating participants ;

(3) Participants are participating in other trials.

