2.3 Participant selection

Prior to the study, the researchers should explain the purpose, contents, benefits

and potential risks of the study to all participants clearly and colloquially. Then the participants or their families should sign the informed consent form, otherwise, they will not be included in the trial.

After signing the informed consent form, all participants will receive the following assessment to determine whether they could be included.

- (1) Demographic data and medical history;
- (2) Vital signs: respiratory rate, heart rate, blood pressure, and body temperature;
- (3) Laboratory examinations: blood routine test, biochemical routine test (including AST, ALT, BUN, Cr, GLU, blood lipid, etc.);
- (4) Electrocardiogram.

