2.4 Grouping

A total of 120 participants will be divided into the healthy control group, COPD group and healthy intervention group., with 40 in each group respectively.

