2.6 Intervention

All the participants are requested to refrain from consuming tea/alcohol/coffee and smoking on the examination day. Besides, exercise and food is also forbidden within one hour before the LDF examination.

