2.3 Statistical analysis

All data in this study will be analyzed by a blinded statistician. Independent sample T test and Chi-square test (χ^2 test) will be used for numerical variables and categorical variables, respectively. When the distribution of variables is abnormal, a non-parametric test will be selected. A P value < 0.05 will be considered statistically significance.

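### Smoking history plays no part in selecting, matching or analysing the COPD and healthy control groups, so the unadjusted site-by-site PU comparison is open to confounding by long-term smoking

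*Combined protocol and SAP*

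**What the plan says.** Part 2, section 1.1.1 (diagnostic criteria for COPD) remarks that "Patients often have a history of exposure to various risk factors"; smoking is not named there. Section 1.2.2 admits healthy volunteers aged 20 or over whose medical report confirms that "they have not any cardiovascular, respiratory, digestive, urinary, hematological, endocrine and neurological disease". Their exclusions in section 1.3.2 cover mental illness and substance misuse ("Participants have mental illness, severe depression, alcohol dependence or history of drug abuse"), pregnancy or lactation, and participation in other trials. Smoking history appears in neither group's criteria.

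Section 2.4 forms the groups as follows: "A total of 120 participants will be divided into the healthy control group, COPD group and healthy intervention group., with 40 in each group respectively". No matching is described. Screening in Part 2, section 2.3 collects "Demographic data and medical history" without naming smoking.

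The one mention of smoking is in section 2.6: "All the participants are requested to refrain from consuming tea/alcohol/coffee and smoking on the examination day".

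Part 3, section 2.3 plans "Independent sample T test and Chi-square test" for numerical and categorical variables respectively, a non-parametric test where the distribution is not normal, and significance at P < 0.05. It names no covariate and no contrast between meridians.

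**The concern.** Having COPD cannot be assigned, so the COPD-versus-control comparison is observational and depends on the two groups being alike in whatever else affects skin blood flow. The protocol expects risk-factor exposure to be common among the patients and does nothing to bring controls with a similar history into the study. The examination-day rule standardises recent intake. It does not equalise years of exposure, and it places only current smokers in short-term abstinence while PU is recorded.

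PU at the Heart and Lung meridian sites is a primary outcome, and this is the only between-group comparison that includes people with diseased lungs. If long-term smoking shifts PU and the groups differ in smoking, the unadjusted difference at a site mixes the two influences. With separate tests at four sites, a pattern of significance at a Lung site and not at a Heart site could be taken for site specificity when it comes from a shift common to both, plus chance.

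The within-person moxibustion comparison in the healthy intervention group is not affected.

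**Working it through.** **The plan's own figure.** Part 2, section 2.2 gives 120 participants (40 COPD, 80 healthy), based on similar studies and practical conditions. There is no effect size, SD or power, so there is nothing to reproduce. For orientation, 40 per group gives about 80% power for a standardised difference of 0.63 (two-sided 5%; the SAP does not state sidedness).

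**Inputs.** From the documents: n = 40 per group, unadjusted two-sample test, alpha 0.05. Assumed, because the documents give no smoking figures: ever-smokers 70–80% in COPD and 10–30% in controls; smoking shifts PU by 0.2 to 0.6 SD; no effect of COPD itself.

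**Step 1, bias at one site.** Bias = (smoking prevalence in COPD − prevalence in controls) × smoking effect in SD.
- Low: (0.70 − 0.30) × 0.2 = 0.08 SD
- Middle: (0.80 − 0.30) × 0.4 = 0.20 SD
- High: (0.80 − 0.10) × 0.6 = 0.42 SD

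**Step 2, rejection at one site with no disease effect.** Noncentral t, df = 40 + 40 − 2 = 78, noncentrality = bias × √(40/2):

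| Bias (SD) | Noncentrality | Rejection |
|---|---|---|
| 0.08 | 0.36 | 6.4% |
| 0.20 | 0.89 | 14.3% |
| 0.42 | 1.88 | 45.8% |

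The low case is not a floor. With 70% v 50% and 0.2 SD, the bias is 0.04 SD and rejection is 5.4%.

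**Step 3, the misreading that bears on site specificity.** Suppose smoking shifts a Lung site and a Heart site equally, with within-person correlation 0.3 to 0.6 (assumed). Simulating one pair of sites, each tested separately, and also the Lung-minus-Heart difference compared between groups:

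| Common bias (SD) | Lung significant, Heart not | Lung-minus-Heart contrast rejects |
|---|---|---|
| 0 | 4–4.5% | 5% |
| 0.08 | about 5% | 5% |
| 0.20 | 8–11% | 5% |
| 0.42 | 15–20% | 5% |

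The contrast keeps its error rate because an equal shift cancels within each person.

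**Step 4, cost of adjusting without matching.** The standard error of the group effect grows by 1/√(1 − φ²), where φ is the correlation between group and smoking.
- 70% v 30%: φ = 0.40, factor 1.09
- 80% v 30%: φ = 0.50, factor 1.16
- 80% v 10%: φ = 0.70, factor 1.41

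If overlap almost vanishes (90% v 0%), the variance inflates 5.5 times and adjustment is not practical at 40 per group.

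**The case against.** The strongest reply is that the design contains its own comparator. Section 2.6.3 measures HT7 and HT3 alongside LU9 and LU5 in both groups, and the stated aim is site specificity. An equal shift at all four sites cannot produce a true Lung-minus-Heart difference. That is right, and it limits the harm. It protects the trial only if that contrast is what gets tested, and Part 3, section 2.3 specifies no such test. It also assumes smoking acts equally at every site, which the documents do not address.

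Second, every smoking input is assumed. Section 1.1.1 speaks only of various risk factors. Section 2.6 lists smoking with tea, alcohol and coffee as same-day standardisation, which does not show that the protocol regards long-term smoking as altering PU. This stands: the sizes are conditional, and with a modest imbalance the effect is close to nil.

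Third, smoking may be recorded under medical history. The case report form is not in the documents, so this cannot be settled; what can be shown is that no use of it is planned.

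Fourth, age (35–75 in COPD; 20 or over with no upper limit in healthy volunteers) and medication (section 2.6.4: patients keep their regimen, healthy volunteers take none) also differ. This stands too: handling smoking alone would not make the groups comparable.

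**Conclusion.** The omission is clear from the text: smoking history has no role in eligibility, group formation or analysis, and the one smoking rule covers acute exposure only. If long-term smoking shifts PU, the unadjusted single-site comparison is biased by 0.08 to 0.42 SD under the assumed ranges.

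Three stronger readings are tempting and not supported. A reader might infer that up to 46% of such trials would report a false Lung-meridian finding. That figure is any rejection at one site; the Lung-but-not-Heart pattern for one pair of sites reaches at most about 20% under these assumptions. A reader might infer that smoking is known to have altered PU in these patients; the documents give no prevalence, size or direction. A reader might also infer that dealing with smoking would allow a difference to be attributed to the lung; age and medication still stand in the way.

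The change should be made because it is cheap and because matching cannot be added once participants are enrolled. Confidence that the gap exists is high. Confidence in its size is limited by the assumptions.

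**What to change.** - **Part 2, section 2.3, item (1):** record current, former or never smoking and pack-years for every participant.
- **Part 2, sections 1.2.2 and 2.4:** frequency-match the 40 healthy controls to the COPD group on smoking status, together with age and sex.
- **Part 3, section 2.3:** for COPD versus healthy control, replace the unadjusted t test with a linear model containing smoking status and age. Name the group-by-meridian (Lung-minus-Heart) contrast as the test of site specificity. Add a sensitivity analysis in ever-smokers only, and use pack-years to describe how far exposure differs among them.
- **Reporting:** state that the medication difference remains and word any attribution to the diseased lung accordingly.

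The cost is a few screening questions, slower recruitment of healthy smokers and ex-smokers of suitable age, and a slightly larger model. The total of 120 need not change. Matching avoids most of the precision loss in step 4; without it the standard error would be 1.09 to 1.41 times as large under the assumed prevalences. Smoking overlap should be checked during recruitment, since adjustment cannot rescue groups that barely overlap.

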2.1 Study design

This is a prospective and open-label clinical trial. The time frame of the trial ranges from July 2019 to December 2020. A total of 120 participants will be divided into the healthy control group, COPD group and healthy intervention group., with 40 in each group respectively.

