2.6.3 Procedures for LDF examination and moxibustion intervention

A four-channel LDF (PeriFlux System 5000, Sweden) will be used to measure the microcirculatory characteristics of meridian phenomena for the Heart and Lung meridians, which could monitor 4 measuring sites simultaneously. The participants will be asked to stabilize for 15 minutes in a supine position in the experimental room before formal examination. They will be informed to keep silent and normal breath and avoid limb movement during the whole measuring period. The probes will be left at relevant measuring sites. Blood flow curve will be recorded constantly using Perisoft software (PeriFlux, Sweden). Perfusion units (PU) of microcirculatory flux in the measuring sites will be calculated by the software [PU = concentration of moving blood cells (CMBC) × velocity (V)].

(1) Healthy control group and COPD group

The probes will be left at 4 measuring acupoints, which include Shenmen (HT7) and Shaohai (HT3) of the Heart meridian, Taiyuan (LU9) and Chize (LU5) of the Lung meridian. The blood flow curve and PU will be recorded for 5 minutes.

(2) Healthy intervention group

Two sessions of moxibustion intervention will be performed in the Heart meridian and Lung meridian successively. The washout period between the two sessions is at least one day.

1) Intervention in the Heart meridian: By igniting the moxa stick and inserting it into a homemade moxibustion holder to adjust the appropriate angle and height, moxibustion will be performed above Shaohai (HT3) of Heart meridian for 15 minutes. During moxibustion, the probes will detect the blood flow curve and PU in four sites in two meridians, which include Shaohai (HT3) of the Heart meridian, the midpoint of the Heart meridian along the left forearm (i.e. the midpoint of the line

between HT3 and HT7), Chize (LU5) of the Lung meridian, and the midpoint of the Lung meridian along the left forearm(i.e. the midpoint of the line between LU5 and LU9). The measuring time points include 5 minutes before moxibustion, 15 minutes during moxibustion and 5 minutes after stopping moxibustion.

2)Intervention in the Lung meridian: The moxibustion acupoint is Chize (LU5) of the Lung meridian. The LDF examination, moxibustion procedure, measuring sites and time points are the same as 1).

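### Healthy controls may be any age from 20 while COPD patients are 35–75; with no matching described and only unadjusted tests named, an age or sex imbalance in the COPD versus control comparison of PU would go uncorrected

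*Combined protocol and SAP*

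**What the plan says.** **Eligibility.** Part 2, 1.2.1 sets a COPD age range from 35 up to "75$ years, male or female". Section 1.2.2 gives healthy volunteers only a lower limit, "20$ years, male or female", and requires a recent medical report showing that they "have not any cardiovascular, respiratory, digestive, urinary, hematological, endocrine and neurological disease".

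**Design.** Section 2.1 says "This is a prospective and open-label clinical trial". Section 2.4 says "A total of 120 participants will be divided into the healthy control group, COPD group and healthy intervention group", with 40 in each. Neither section mentions matching, quotas or stratification, and nor do the healthy-volunteer exclusions (1.3.2) or the recruitment section (1.4). Section 2.3 collects demographic data and medical history at screening to decide inclusion; no use of them in the analysis is stated.

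**Measurement.** Section 2.6.3 places "Healthy control group and COPD group" under one procedure: PU for 5 minutes at HT7, HT3, LU9 and LU5. Section 3 makes PU a primary outcome.

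**Analysis.** Part 3, 2.3 names "Independent sample T test and Chi-square test", plus an unspecified non-parametric test for non-normal data. It names no covariate, no model and no particular contrast between groups.

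**The concern.** COPD and healthy control participants differ by disease status, not by random allocation, so comparability has to come from selection or from the analysis. The available text provides neither. A control group made up entirely of people aged 20 to 34 would meet every criterion and share no ages with the patients. The criteria do not force such an imbalance, but nothing in them prevents it.

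If PU at a site varies with age or sex, the COPD versus control test at that site can reject when COPD has no effect. Enrolling more participants would not help; it would only estimate the biased difference more precisely. Nor can an adjustment be assumed later: under Part 2, 2.5 the statisticians are to be blinded to the protocol, so they would have only the SAP's unadjusted tests to follow.

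**Working it through.** There is no planned figure to reproduce. Section 2.2 sets 120 participants by reference to similar studies and feasibility, without an effect size, SD or power. The calculation below only gives a sense of scale.

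**From the documents:** 40 per group; ages 35–75 (COPD) and 20 or older (healthy); significance level 0.05. **Assumed:** a two-sided test, a PU–age slope of 0.1 to 0.2 SD per decade, a sex difference of 0.2 to 0.4 SD, and no COPD effect.

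**Method.** An imbalance shifts the group difference by b SD, where b = (age gap / 10) × slope. The t statistic then has 40 + 40 − 2 = 78 df and noncentrality b × √(40/2) = 4.47b. The rejection rate is the probability beyond the two-sided 5% critical values.

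**Even recruitment.** Mean ages are (35 + 75)/2 = 55 and (20 + 75)/2 = 47.5, a gap of 7.5 years. Controls are taken to 75, although the text sets no upper limit.

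| Age gap (years) | b at 0.1 SD/decade | Rejection rate | b at 0.2 SD/decade | Rejection rate |
|---|---|---|---|---|
| 7.5 | 0.075 | 6.3% | 0.15 | 10.2% |
| 10 | 0.10 | 7.3% | 0.20 | 14.3% |
| 20 | 0.20 | 14.3% | 0.40 | 42.4% |
| 30 | 0.30 | 26.3% | 0.60 | 75.5% |

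The 30-year row is permitted by the criteria, but nothing in the text points to it.

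**Sex.** A 30–40 point difference in the share of men, times 0.2–0.4 SD, gives b = 0.06 to 0.16 and rejection rates of 5.8% to 10.9%.

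**Simulation** (6,000 runs, linear age effect, residual SD 1). The pairs are for slopes of 0.1 and 0.2 SD per decade.

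- Even recruitment: 6.2% and 9.3% unadjusted; 5.1% and 5.1% adjusted for age and sex.
- Same age range but unmatched (patients spread over 55–75, controls over 35–75, a 10-year gap): 7.7% and 14.7% unadjusted; 5.0% and 5.1% adjusted.

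A common age range alone is therefore not enough.

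**Power cost of adjustment.** At an assumed effect of 0.63 SD, the unadjusted test has power 0.795. Adjusting for age and sex uses 2 df, which gives 0.794 if the groups are matched. If they are not, the variance of the group difference is inflated by 1 + (gap / age SD)²/4. With an assumed within-group age SD of 10 to 12 years:

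| Age gap (years) | Variance inflation | Power |
|---|---|---|
| 3 | 1.02 | 0.785–0.788 |
| 7.5 | 1.10–1.14 | 0.740–0.757 |
| 10 | 1.17–1.25 | 0.701–0.728 |
| 20 | 1.69–2.00 | 0.503–0.570 |

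The age SD matters. Even recruitment implies SDs of 40/√12 = 11.5 and 55/√12 = 15.9 years (pooled 13.9), hence inflation 1.07 and power 0.766. The 55–75 versus 35–75 case implies a pooled SD of 9.1, hence inflation 1.30 and power 0.684. The conclusion is the same: match first, then adjust.

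**The case against.** **The contrast is inferred.** Part 3, 2.3 names none. An objective in Part 1 is to "investigate the site specificity for the meridian-visceral association", and a within-person Lung-minus-Heart difference serves it more directly than a group difference at one site. Confounding that is equal at all four sites cancels in that difference, and its error rate stays at 5%. This limits the concern to single-site group comparisons. It does not remove it, because no Lung-minus-Heart analysis is prespecified, while a group called healthy control, a shared recording procedure and an independent-sample test all point to a group comparison.

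**The sizes are assumed.** This stands. The scenario closest to the eligibility text gives 6–10%, which is modest; the large rates need gaps that the text allows but does not predict. The sex component is weaker still, since both criteria admit either sex and the assumed difference in the share of men has no source in the documents.

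**Matching may be described elsewhere.** The study flow diagram is not reproduced in the available copy, so the finding is limited to the available text.

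**Age and sex are not the only differences.** Healthy volunteers must be free of listed diseases and take no medication. Patients keep their treatment and are excluded only for some conditions. Matching and adjustment for age and sex leave these differences in place. That limits what a COPD versus control difference can show, but is no reason to leave age and sex uncontrolled.

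**Conclusion.** The concern holds and should be fixed. The age limits differ, the available text describes no matching, and only unadjusted tests are named, so following the plan exactly can give a biased COPD versus control comparison of a primary outcome. Confidence is high on these facts. How large the bias would be is unknown: on the assumptions above, a nominal 5% test runs at about 6–10% under even recruitment and up to 42% with a 20-year gap. This applies to a group comparison at a single site. It would not apply to a Lung-minus-Heart contrast if confounding were equal at all sites.

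**What to change.** 1. **Selection.** Restrict the healthy control group to 35–75 years and frequency-match it to the COPD group on age band and sex, with the bands stated in advance. Group sizes stay 40/40/40. Younger volunteers can enter the healthy intervention group, which is recorded before, during and after moxibustion. That would create an age difference between the two healthy groups, so if they are to be compared with each other, both need the same age range.
2. **Analysis.** Prespecify a linear model for COPD versus control PU, adjusted for age and sex, with the unadjusted test as a sensitivity analysis. Fix the rule for log-transforming skewed PU in advance. State whether the claim is the group difference at each site or the group-by-meridian (within-person Lung versus Heart) difference.
3. **Smoking.** Record smoking history as a named case report form item, since medical history may or may not capture it, and adjust for it only as a sensitivity analysis. Taken separately from age, with 3 df used, ever-smoker shares of 70% v 30% give inflation 1.19 and power 0.722; 80% v 25% give 1.44 and 0.641. These shares are assumptions.

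**Cost.** One eligibility or grouping sentence, one SAP paragraph and one form item. Control recruitment may be slower, because older volunteers must also be free of the listed diseases. With matching, the loss of power from age and sex adjustment is negligible (0.795 to 0.794).
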